1.3 Research hypothesis

A structured training programme based on action research is more effective than traditional training in improving collaboration among healthcare professionals working in Cardiac Intensive Care Units (UTICs), including physicians, nurses, healthcare assistants (OSS), students and newly hired staff.

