1.5 Study design

The study design is longitudinal and prospective and provides for the evaluation of the effectiveness of an interprofessional training pathway through three assessment points: before the intervention (T0), immediately after completion of the programme (T1) and six months later (T2). The evaluation will be carried out exclusively on healthcare professionals who have completed the training and are still working in the unit at the time of the six-month follow-up.

The intervention consists of a training programme specifically designed to improve collaboration among healthcare professionals working in Cardiac Intensive Care Units (UTICs), using active and context-based methodologies.

At each time point the same indicators are collected, including perception of collaboration, attitude towards collaboration, decision-making, team and professional commitment, and self-efficacy. These dimensions constitute the primary outcomes of the intervention and are observed to measure the evolution over time of behaviour and professional perceptions of the staff involved.

The design also takes into account several socio-demographic and professional variables—such as age, gender, years of service, professional role and previous participation in courses on collaboration—that may influence the impact of the training pathway. For students, the degree course (medicine or nursing) and academic year are also recorded. These factors are collected at baseline (T0) and will be used for possible subgroup or adjusted analyses.

Before the start of the training pathway, a detailed guide on how to access the platform will be distributed.

Overall, the design aims to assess not only the immediate effectiveness of the training path but also its sustainability over time, by observing changes in professional behaviours and attitudes six months after the intervention.

2. Methodology: participants, interventions and endpoints

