2.3 Interventions

2.3.1 Experimental intervention – Training phase

The training phase of the project consists of an interactive course aimed at healthcare professionals (physicians, nurses and OSS) to improve their ability to recognise and enact effective collaborative practices. Learning is based on the use of **branching scenarios**, created with the H5P software. This approach enables learners to distinguish correct practices and refine their teamwork skills. The course also provides access to additional content on techniques and procedures specific to the UTIC context, curated by expert professionals.

Branching scenarios – Learning scenarios

The branching scenarios reproduce complex and frequent clinical situations that challenge interprofessional collaboration. Each scenario has been designed with particular attention to clinical and organisational details, including:

- the clinical history of the simulated patient and their clinical pathway in the cath-lab and electrophysiology unit, in preparation for a TAVI procedure, with a diagnosis of heart failure (Annex 1);
- vital signs and diagnostic tests;
- available resources;
- clinical objectives and potential critical points.

The structure of each scenario includes:

- definition of a storyline and of the role of the professional involved;
- division into key phases, with information and possible actions, and the related consequences;
- interactive elements that enable the learner to make decisions and interact with characters or objects in the scenario;
- meaningful feedback guiding the learning process;
- multiple paths for a dynamic experience;
- assessment criteria based on the correctness of the responses.

For validation and revision of these scenarios, a team of content experts and educationalists was involved to verify the accuracy, relevance and effectiveness of the material. Pilot tests with sample users were also carried out to collect feedback on usability and clarity, and the necessary modifications were implemented.

Four training pathways are planned, each lasting six months:

1. Cath-lab pathway
2. Electrophysiology pathway
3. Heart failure pathway
4. TAVI pathway

For further details on the structure of the pathways, see Annex 8 “Pathway Sheets”.

Platform and technical implementation

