3.2 Data analysis

- **Reliability and validity:** At T0, T1 and T2 Cronbach's alpha and McDonald's omega will be calculated for each (sub)scale. Where appropriate, the factor structure will be confirmed through confirmatory factor analysis (CFA) with assessment of measurement invariance (configural → metric → scalar) prior to longitudinal comparison.
- **Data preparation and quality:** data cleaning, coding, reverse-scoring of items; exploration of missing data, outliers and distributions (histograms, Q–Q plots); inspection of floor and ceiling effects; documentation of the data dictionary.
- **Descriptive analysis and responsiveness:** descriptive statistics for T0, T1 and T2 (mean, SD, median, IQR) for total and subscale scores. Suggested graphs: spaghetti plots (individual trajectories), box/violin plots and mean lines with 95% CI over time. Responsiveness to change: calculation of Cohen's d (T1–T0; T2–T0; T2–T1) and Standardized Response Mean (SRM) as indices of change, with interpretation according to literature conventions; where possible, definition/search of MCID.
- **Main analysis – Linear mixed models (LMMs):** For each outcome, a linear mixed model will be used with time as a within-subject factor.
 - Dependent variable: continuous outcome score.
 - Fixed effects: Time (T0 as reference; levels T1, T2).
 - Random effects: random intercept for participant; if data allow, random slope for Time.
 - Covariance structure: unstructured or AR(1) for equally spaced measures; REML estimation.
 - Planned contrasts: T1–T0 (immediate effect), T2–T0 (maintenance), T2–T1 (decay/maintenance).
 - Effect measures: standardised β , marginal and conditional R^2 ; conversion to d from LMM estimates with 95% CIs.

- Assumptions/diagnostics: normality of residuals and homoscedasticity; graphical inspection and robust tests in case of violations.
- Covariates (recommended): age, seniority, profile (physician, nurse, OSS, student/new hire), concurrent educational exposures.
- Interactions: Time × Profile; Time × Seniority, to analyse differential impacts.
- Clustering: if relevant (e.g. shifts/teams), addition of a group-level random effect.

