5.4 Informed consent

Informed consent will be obtained by the PI or a delegate when healthcare professionals and medical/nursing students first enter the UTIC unit.

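### With no untrained comparison, Time × Profile and Time × Seniority cannot separate a differential training effect from newcomers settling into the unit, so section 3.2 should not read them as differential impact

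*Protocol*

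**What the plan says.** Section 3.2 of the protocol specifies a linear mixed model for each outcome, with time as the fixed effect and a random intercept per participant. It adds "Interactions: Time × Profile; Time × Seniority, to analyse differential impacts". The levels of Profile appear in the covariate line: "Covariates (recommended): age, seniority, profile (physician, nurse, OSS, student/new hire), concurrent educational exposures". Students and new hires therefore form one level, set against physicians, nurses and OSS.

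Section 1.5 describes one trained group assessed "before the intervention (T0), immediately after completion of the programme (T1) and six months later (T2"). No comparison group appears anywhere, although the hypothesis in 1.3 is that the programme "is more effective than traditional training in improving collaboration among healthcare professionals working in Cardiac Intensive Care Units (UTICs"). That hypothesis explicitly covers newcomers: "including physicians, nurses, healthcare assistants (OSS), students and newly hired staff".

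On timing, section 2.3.1 states "Four training pathways are planned, each lasting six months". Section 5.4 says "Informed consent will be obtained by the PI or a delegate when healthcare professionals and medical/nursing students first enter the UTIC unit". Section 2.7 instead has consent requested on the training days from people already affiliated with the unit, and section 3.1 ties T0 to the start of the training event. Section 2.2.1 admits students whose placement is under way or already finished. Section 1.5 lists years of service among the baseline variables, but not time in this unit.

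**The concern.** When everyone is trained, an interaction of time with a baseline characteristic shows only that one kind of participant changed more than another. Calling that differential impact assumes that nothing other than the training makes the groups change differently.

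For newcomers that assumption is doubtful. If T0 falls near "when healthcare professionals and medical/nursing students first enter the UTIC unit", the six months to T1 are also the first six months in the team. Several outcomes in section 2.4 are ones that could move in that period without a course: commitment to the unit or team, felt competence at work, and how often one reports collaborating. Established staff are past that stage.

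At stake is a conclusion that the programme works better in students, new hires or junior staff, when the data could show the same pattern with no training effect. To a smaller degree, the pooled Time contrasts could carry part of the same gain.

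**Working it through.** **1. Is there anything in the plan that separates the two explanations?**

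- There is no untrained or traditionally trained group, no repeated measurement before training and no staggered start (1.5, 3.2).
- Profile and seniority as covariates adjust the level of the outcome, not its change over time.
- A random slope describes individual variation and does not remove a mean shift in one group.
- Concurrent educational exposure is only a recommended covariate and is not defined. Induction would largely coincide with being a new hire.
- No minimum time in the unit at T0 is set (2.2.1, 2.2.2).

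For someone enrolled at entry who follows one pathway, T0 to T1 is 6 months and T0 to T2 is 6 + 6 = 12 months, about the first year in the unit.

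**2. Inputs.** From section 2.6: 5 + 30 + 8 = 43 staff and 5 + 5 = 10 students, 53 in all. The number of new hires is not given. The protocol has no power calculation and no figure for the interactions, so there is no stated figure to reproduce. Assumptions, none from the documents:

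- training effect zero in everyone;
- a favourable settling-in gain g, in outcome SDs, from T0 to T1 in the student/new-hire level only;
- within-person correlation ρ of 0.5 or 0.7;
- two-sided 5% level.

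Physicians, nurses and OSS are merged for the comparison.

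**3. What Time × Profile estimates.** Expected contrast = (0 + g) − (0 + 0) = g. Simulation (8,000 runs per setting) agreed: mean estimates were 0.30, 0.50, 0.80 and 1.00 for g = 0.3, 0.5, 0.8 and 1.0. If only half of the level is settling in, the expectation is g/2.

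**4. How often it would reach p<0.05.** SD of change = √(2(1−ρ)), which is 1.00 at ρ = 0.5 and 0.775 at ρ = 0.7. The standard error of the contrast for 10 against 43 is SD of change × √(1/10 + 1/43) = SD of change × 0.351, so 0.351 and 0.272.

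| g (SD) | 10 v 43, ρ 0.5 / 0.7 | 15 v 38, ρ 0.5 / 0.7 | 10 v 43, half settling in, ρ 0.5 / 0.7 |
|---|---|---|---|
| 0 | 5% / 5% | 5% / 5% | 5% / 5% |
| 0.3 | 13% / 20% | 16% / 25% | 7% / 9% |
| 0.5 | 30% / 45% | 37% / 56% | 11% / 15% |
| 0.8 | 63% / 84% | 75% / 92% | 21% / 29% |

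The first two result columns come from the power formula. A t-test simulation of the 10 v 43 case gave similar values (29% / 43% at g = 0.5). The last column is simulated. The 15 v 38 column assumes that five of the 43 staff are new hires.

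**5. Pooled T1−T0 contrast.** Inflation = (k/N) × g, where k is the number settling in:

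- 10 students of 53: 10/53 × 0.3 to 0.8 = 0.06 to 0.15 SD.
- 5 new hires of 43 staff (assumed count): 5/43 × 0.3 to 0.8 = 0.03 to 0.09 SD.
- 15 of 53 (same assumed count): 15/53 × 0.3 to 0.8 = 0.08 to 0.23 SD.

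**The case against.** The strongest reply is that the overlap between settling in and training is possible but not established. Section 5.4 is the only place that puts enrolment at entry to the unit. Section 2.7 has consent taken on training days from people already affiliated, and section 3.1 anchors T0 to the training event. Taken literally, 5.4 cannot fit staff already in post. Section 2.2.1 admits students who have finished their placement and are no longer settling in. All of this stands. It limits how many participants are affected, though a new hire is by definition a recent entrant under either consent rule.

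Second, years of service is not stated to be time in this unit. A long-serving nurse may be new to the UTIC, and one with short service may be well settled. A reader might infer that low seniority and concurrent induction are the same variable; the documents do not support that, and the Time × Seniority argument is indirect.

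Third, a reader might infer that the interactions would show differential impact even if the training did nothing. That goes too far. It needs a gain that the documents do not quantify, and even a 0.5 SD gain would more often than not miss significance with 10 people in the level. The supportable word is could.

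Fourth, it is unclear whether students enter the pooled contrast. Section 1.5 confines the evaluation to professionals still working in the unit, and 2.3.1 aims the course at physicians, nurses and OSS. If students are out, only new hires contribute to the inflation.

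Finally, these analyses are exploratory (1.4.2, and the subgroup remark in 1.5), and the missing comparator affects every Time contrast. Both are true, but section 3.2 still writes a causal reading into the plan, and settling in is a specific consequence that can be handled separately.

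**Conclusion.** The concern holds as a limit on interpretation. Time × Profile and Time × Seniority estimate differences in change from all causes, and settling in is a credible rival cause for participants enrolled near their entry to the unit. The point is most direct for Time × Profile, weaker for Time × Seniority, and does not apply to students with a finished placement.

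With no training effect, the Time × Profile estimate is centred on the settling-in gain, or on half of it if half the level is settling in. Whether that would be visible depends on a gain and a number of newcomers that the protocol does not give. The effect on the pooled contrast is modest across most of the assumed range; the top figure of 0.23 SD needs both the largest assumed gain and an assumed count of new hires.

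A reader might also conclude that the effectiveness contrasts must be confined to established staff. The documents do not support that as a correction: section 1.3 puts students and new hires inside the hypothesis, and a restricted contrast would still be uncontrolled. A sensitivity analysis is the proportionate answer.

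**What to change.** - In section 3.2, replace the purpose given for the interactions with: *to describe differences in change over time, which cannot be attributed to the training because settling into the unit may be concurrent*.
- Record months in this unit at T0, in addition to years of service.
- Keep the all-participant Time contrasts as the main analysis. Add a pre-specified sensitivity analysis of the same contrasts in established staff, for example those with at least six months in the unit at T0, which matches the length of one pathway. Show new hires and students separately as well.
- Reconcile sections 2.7 and 5.4 on when consent is taken, so that the position of T0 relative to unit entry is clear.

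The cost is a few sentences and one baseline item, which has to be in place before T0 data are collected. The sensitivity estimate will rest on fewer people and be less precise.

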3.3 Data protection and confidentiality

Data will initially be collected using paper forms (see annex) and then entered into an electronic database by the PI or a delegate. The electronic quantitative data file will be accessible only to the Promoter and their delegates and stored on password-protected company computers. Data will be pseudo-anonymised. In the event of a confirmed breach, the folder path will be changed and the members of the study group indicated in the protocol will be asked to change their password.

4. Monitoring

Quality monitoring of the study, given that the promoter is the University Hospital of Parma itself, will be carried out by the Quality Assurance (QA) unit, part of the Clinical and Epidemiological Research Unit, as specified in the Clinical Monitoring Regulation (protocol no. 0024107 of 04/06/2024).

5. Ethical considerations and communications

Informed consent will be obtained from all healthcare professionals involved, including medical and nursing students, in accordance with current regulations. For this research protocol and its related informed consent documents, a request for approval will be submitted to the local Ethics Committee in order to verify scientific adequacy and full compliance with ethical and research regulations protecting participants.

5.1 Ethical approval and study start

The study will be conducted in accordance with this protocol and will start only after Ethics Committee approval and subsequent authorisation by the General Directorate. Health Professions Directorate will be informed before the beginning of the study. Data for research purposes will be collected on a voluntary basis.

5.2 Gantt chart

The protocol includes a Gantt chart (page 21 of the original document) detailing responsibilities and estimated duration for all phases: drafting of the protocol, ethics approval, scenario development and validation, Moodle platform development and testing, recruitment and consent, data collection at T0–T1–T2, training delivery, data digitisation and analysis, quality monitoring, report writing and dissemination of results over a 24-month period.

5.3 Protocol amendments

Any modifications to this protocol will be promptly communicated by the PI to the Ethics Committee and to the participants.

5.4 Informed consent

Informed consent will be obtained by the PI or a delegate when healthcare professionals and medical/nursing students first enter the UTIC unit.

5.5 Confidentiality

Data collection sheets, initially in paper format, will subsequently be digitised and will be accessible only to the PI and delegates, stored on password-protected computers of the University Hospital of Parma. Paper forms will be destroyed after digitalisation.

Data will be pseudo-anonymised. In the event of a confirmed breach, the folder path will be changed and the study team members listed in the protocol will be asked to change their password.

5.6 Conflict of interest

Members of the research group declare that they have no conflicts of interest or financial interests of any kind related to this protocol.

5.7 Data access

Access to the study data will be strictly limited to the Principal Investigator and their delegates. Data will be anonymised before analysis. Anonymised raw data will be stored in a secure database on a server of the University Hospital of Parma, protected by password and accessible only to the Principal Investigator and their delegates.

5.8 Dissemination policy

At the end of the study, the research group will assess the most appropriate modes of dissemination of the results. In particular, publication of one or more articles in peer-reviewed journals will be considered. In addition, the organisation of a dedicated educational event for professionals internal and external to the University Hospital and the University of Parma will be evaluated, with the aim of sharing the evidence produced and promoting a culture of interprofessional collaboration in CICU/UTIC settings.

5.9 Expected results / Impact of the study

The success of this project will be evaluated based on the effectiveness of the training intervention on the perception of collaboration and attitudes towards teamwork.

The following results are hypothesised at the end of the intervention:

- **Improved perception of collaboration:** an improvement in perceived interprofessional collaboration among the professionals involved is expected.
- **Positive change in attitudes:** an increase in mean scores on questionnaires assessing attitudes towards collaboration, reflecting a greater propensity to work jointly for the patient's benefit.
- **Increased knowledge and skills:** participants are expected to show greater awareness of the importance of interprofessional collaboration and to acquire new skills to address barriers to teamwork.
- **Development of a “community of practice”:** the project is expected to foster the creation of a stable network among professionals, who will continue to exchange knowledge and collaborate even after the end of the study, consolidating a lasting culture of collaboration within the UTIC.
- **Strengthening of team cohesion:** participants are expected to report increased trust and confidence in group dynamics, a greater sense of synergy in daily work and a reduction in communication inefficiencies, resulting in better interprofessional collaboration and a stronger sense of team—essential for the complex management of patients in Cardiac Intensive Care.
- **Increased professional commitment:** the experience of effective collaboration and the perception of contributing meaningfully to shared goals are expected to strengthen participants' professional

commitment, leading to higher job satisfaction and a reduction in stress and burnout factors related to communication, as well as a stronger sense of value and identification with their role within the team.

6. References

1. Agenzia Sanitaria e Sociale regione dell'Emilia Romagna. (2017). Accompagnare le persone nei processi di cambiamento- Linee di indirizzo regionali per progettare e realizzare la formazione continua in sanità.

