2.4 Endpoints

Description of endpoints, instruments, measurement units and frequency

- **Attitudes towards interprofessional collaboration**
 - Instrument: *Jefferson Scale of Attitudes toward Physician–Nurse Collaborative Relationships (JSAPNC)*.
 - The instrument consists of 5 dimensions: (1) shared education, (2) teamwork, (3) caring vs. curing, (4) nurse autonomy, (5) physician autonomy. It includes 15 items on a 4-point Likert scale from 1 = “strongly agree” to 4 = “strongly disagree”.
- **Perception of collaboration**
 - Instrument: *Nurse–Physician Collaboration Scale (NPCS)*.
 - The scale consists of 3 dimensions: (1) joint participation in the care-related decision-making process; (2) sharing of patient-related information; (3) cooperativeness. It includes 20 items on a 5-point Likert scale (1 = always, 2 = usually, 3 = sometimes, 4 = rarely, 5 = never).
- **Decision-making**
 - Instrument: *Collaboration and Satisfaction with Care Decisions (CSACD)*.
 - The tool measures collaboration between physicians and nurses in decision-making about patient care in relation to a specific patient. It consists of 8 items: the first seven measure interaction, and the last measures satisfaction with the decision-making process, on a 5-point Likert scale from “strongly disagree” to “strongly agree”.
- **Team and professional commitment**
 - Instrument based on items adapted from Ellemers et al. (1995), Cadinu & Reggiori (2002) and Le Blanc et al. (2010).
 - Total of 17 items: 12 items for **professional commitment** (e.g. “In general, I am happy to be part of my professional category”) and 5 items for **team commitment** (e.g. “I am satisfied to be a member of this unit/team”), on a 5-point Likert scale from 1 = strongly disagree to 5 = strongly agree.
- **Self-efficacy**
 - Instrument: “Personal accomplishment” subscale of the *Maslach Burnout Inventory (MBI)*, Italian adaptation by Vanin & Castelli (2003) and Sirigatti & Stefanile (1993), based on Maslach & Jackson (1981).
 - Composed of 5 items evaluating perceived competence and personal accomplishment at work, using a 5-point Likert scale from 1 (strongly disagree) to 5 (strongly agree). Example item: “I feel very competent in my work.”

Data collection for these endpoints will occur at three time points: before the start of the training (T0), at the end of the training (T1), and six months after completion of the programme (T2).

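### Does the agree-to-disagree coding of the attitude scale (JSAPNC) conflict with counting a rise in mean attitude score as improvement?

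*Protocol*

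**What the plan says.** Three places in the protocol bear on the direction of the attitude score.

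- **Section 2.4 (Endpoints).** The only attitude instrument is the JSAPNC: "15 items on a 4-point Likert scale from 1 = “strongly agree” to 4 = “strongly disagree". The section does not say how the total is formed or which end is favourable.
- **Section 3.2 (Data analysis).** Data preparation includes "data cleaning, coding, reverse-scoring of items", and the same bullet commits to a documented data dictionary. The mixed model then reports signed contrasts, "T1–T0 (immediate effect), T2–T0 (maintenance), T2–T1 (decay/maintenance", alongside Cohen's d and the standardised response mean (SRM).
- **Section 5.9 (Expected results).** Success is to be judged on the "effectiveness of the training intervention on the perception of collaboration and attitudes towards teamwork", and the expected attitude result is "an increase in mean scores on questionnaires assessing attitudes towards collaboration, reflecting a greater propensity to work jointly". The text speaks of questionnaires in general and does not name the JSAPNC.

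The other scales in section 2.4 do not all run the same way. The perception scale (NPCS) uses a "5-point Likert scale (1 = always, 2 = usually, 3 = sometimes, 4 = rarely, 5 = never", commitment is scored "on a 5-point Likert scale from 1 = strongly disagree to 5 = strongly agree" and self-efficacy "using a 5-point Likert scale from 1 (strongly disagree) to 5 (strongly agree".

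**The concern.** If most JSAPNC items are worded so that agreement favours collaboration, a better attitude produces lower codes under the anchors in section 2.4, while section 5.9 calls a higher mean the improvement. The reverse-scoring in section 3.2 names no scale, no items and no final direction. In its ordinary sense it brings oppositely worded items into line with the rest, which could leave the total with low as favourable.

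Attitudes are a primary outcome and one of the two on which section 5.9 says success will be judged. The study has a single group, so the sign of the change over time is what separates benefit from harm. If the total were left with low as favourable and then read against 5.9, a true gain could be taken for a deterioration and a true deterioration for the hoped-for gain. Signs could also differ across the five primary outcomes for the same benefit.

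**Working it through.** The protocol gives no figure to reproduce here. The check asks what each scoring procedure that fits section 3.2 does to the attitude contrast.

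**Inputs.** From section 2.4: 15 items coded 1 to 4, so a summed total runs from 15 × 1 = 15 to 15 × 4 = 60. Assumed, because the protocol does not give them:
- *k*, the number of items worded against collaboration, varied over 0, 2, 5 and 7;
- baseline responses of 2 on favourably worded items and 3 on the others;
- an improvement of 0.2 points per item (range 0.1 to 0.3).

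**Procedure A: reverse only the *k* unfavourably worded items (low = favourable).** Every item starts at 2 and moves to 1.8. Total: 15 × 2 = 30 to 15 × 1.8 = 27. T1−T0 = −3.0 for every *k* (−1.5 to −4.5 over the range).

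**Procedure B: reverse the favourably worded items (high = favourable).** Every item starts at 3 and moves to 3.2. Total: 15 × 3 = 45 to 15 × 3.2 = 48. T1−T0 = +3.0 for every *k* (+1.5 to +4.5).

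**Relation between A and B.** Each item in B is 5 minus the same item in A, so total B = 15 × 5 − total A = 75 − total A. This is a linear reflection. It keeps every variance and covariance. In the mixed model the time effects change sign, while their standard errors, p-values and absolute size stay the same. Cohen's d and SRM keep their size and change sign.

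**No reversal at all.** T1−T0 = −0.2 × (15 − 2*k*):

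| *k* | T1−T0, raw total |
|---|---|
| 0 | −3.0 |
| 2 | −2.2 |
| 5 | −1.0 |
| 7 | −0.2 |

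At *k* = 8 it becomes +0.2, so even the sign of the raw total depends on item wording that the protocol does not show. For any *k* above 0 the raw total also shrinks the effect. This procedure is not the plan, because section 3.2 provides for reverse-scoring. The reliability and factor analyses planned there would also tend to expose items left pointing the wrong way.

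**The sections side by side.** Section 2.4 describes how answers are recorded. Section 3.2 says that recorded answers are coded and reversed before analysis. Section 5.9 says which way the analysed score should move when attitudes improve. Procedure B satisfies all three. Procedure A satisfies 2.4 and 3.2 but not 5.9. A consistent reading therefore exists, and 5.9 is what points to it.

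**The case for a change.** The strongest case for a change is that the protocol prints two directions itself, one in the response codes and one in the expected result, and leaves the bridge between them unstated. Procedures A and B both fit the wording of section 3.2 and give opposite signs, and only B agrees with 5.9. On this view the point is more than omitted scoring detail, since an SAP could choose a coding and still leave the protocol's two statements looking inconsistent. One sentence would settle it before any data are scored, at almost no cost.

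Part of this stands. No section says outright that a higher JSAPNC total is favourable, and the reverse-scoring phrase does not settle it on its own. But response anchors are not a score direction, and a contradiction would need section 2.4 to say that low totals are better, which it does not. Whether agreement is favourable on most items cannot be established from the protocol. Which items are reversed, and toward which end, is scoring-key content that normally sits in an SAP or data dictionary. Only the protocol was available here, and it commits to such a dictionary.

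The mixed anchors of the other scales add little. Different instruments often run in different directions, and for perception section 5.9 predicts an improvement without naming a score direction.

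**Conclusion.** The plan can stand. What remains is an unwritten scoring direction for one of five primary outcomes, and analysts following the protocol would fill it sensibly: the codes are known, reversal is planned, a data dictionary is to record it, and section 5.9 gives the intended direction. To report a real gain as a loss, they would have to overlook both their own coding and their own stated expectation.

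The possible harm is confined to the sign and how it is read. Under the assumed 0.2 points per item it is the difference between −3.0 and +3.0 on a 15-to-60 total, with identical precision and p-value. Section 5.9 is a narrative of expected results with no formal decision rule, so no test or threshold depends on that sign.

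This conclusion assumes that items are aligned with one another before they are summed, as section 3.2 provides. The size of the improvement and the number of unfavourably worded items are illustrative. The equality of size and precision between the two aligned codings depends on neither.
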